The overall goal is to pilot test and establish a procedure for video-assisted alcohol topography and explore its utility as an indicator of alcohol use disorder. Our specific aims include the following: (1) characterize drinking behavioral patterns by converting videotaped drinking episodes into various drinking related parameters (e.g., sipping frequency, sipping intervals, sipping duration, rest duration, sipping amount); (2) compare drinking behavioral patterns across groups defined by drinking status (social vs. heavy drinkers) and mental health status (elevated vs. non-elevated depressed mood); and (3) use advanced nonlinear modeling to quantify the behavioral pattern and to derive potential indicators for alcohol use disorder.

6. Research plan

Overview

There are 4 phases to this study: 1) pre-screening by phone; 2) in-person screening appointment; 3) the first alcohol drinking session with videotaping; and 4) follow-up appointment for retest. The figure below gives a timeline of the steps involved in the study. Each alcohol drinking session including all testing will require 3-4 hours.

Participants

Recruitment: Participants will be recruited through recruiting flyers (Attached) posted on the UF campus and vicinity, along with ads posted on online classified sites such as Craigslist and newspapers. Prospective participants who see one of these

advertisements and are interested in the study will contact the study initially via telephone, text, or email message. Study staff will answer any questions and conduct a preliminary phone screen among those who would like to pursue study participation.

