General inclusion & exclusion criteria: Participants must be 21-55 years of age, able to read English and complete study surveys, report liking beer and consuming it at least once in the past 30 days, and report having consumed at least two alcoholic drinks on at least one day during the past 30 days (i.e., current drinkers). Participants will be excluded if their urine drug test indicates recent use of illegal drugs (except cannabis) and pregnancy for women. In addition women who report engaging in sexual activity with opposite sex partners without use of reliable birth control will be excluded. Participants will also be excluded for any of the following conditions: a history of medically-assisted detoxification; present with signs of current alcohol withdrawal; currently meet the severe threshold for alcohol use disorder according to DSM-5 (i.e., 6 criteria or more); currently meet DSM-5 substance use disorder criteria at any level (i.e., 2 or more criteria) for any substance besides alcohol; are currently seeking treatment for problem substance use; have engaged in intensive outpatient or inpatient treatment for substance use in the past 12 months; meet criteria for severe depression or have any serious psychological or medical history that contraindicates alcohol consumption; currently taking any medication that contraindicates alcohol use at the levels included in this study; and have BMI under 18.5 or over 35. Given that video recording is a critical aspect of the study, participants will be required to agree to video recording in order to take part in the study. Undergraduates enrolled at the University of Florida will be excluded from participating. Graduate and non-matriculating students will be allowed to participate as long as they are not enrolled in the College of Health and Human Performance.

Subgroup division: Participants will be further divided by drinking status (social vs. heavy drinkers) and mental health status (elevated vs. non-elevated depressed mood). This creates four combinations of subgroup category (2×2). Efforts will be made to recruit equal numbers of men and women in each of the 4 categories.

Sample size: As a pilot study, we will target enrollment of up to 40 participants (~10 in each subcategory as defined in the previous section).

Procedure

Pre-screening by phone:

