- a. *Drinking behaviors:* Past 30-day drinking behaviors and DSM-5 criteria for alcohol use disorder will be used as the basis for distinguishing social and heavy drinkers. The social drinker group will be those who (1) consume at least 1 but no more than 5 standard alcoholic drinks per week and (2) engage in infrequent binge drinking (i.e., 5 or fewer times per year, but allowing for 1 past interval of a maximum of 6 months' duration of up to twice weekly binge drinking). The heavy drinker group will be those who (1) consume at least 10 alcoholic drinks per week ; (2) engage in regular binge drinking (i.e., consume 5 or more drinks on one occasion or ≥ 4 for women 1 to 5 times on average per week); and (3) meet DSM-5 criteria for mild or moderate alcohol use disorder. These criteria are based on criteria outlined by King et al.¹⁹ The timeline followback (TLFB) interview will be used to obtain self-reports of drinking behavior with a focus on past-30-day behavior, however the extent to which recent drinking behavior resembles past-12-month and lifetime drinking behavior will be queried in order to make sure participants meet criteria for

one of these two categories. Those who drink but who did not clearly fall into one of these two groups will be excluded from participation.

- b. *Depression:* Patient Health Questionnaire (PHQ-2 and PHQ-9) will be used for depression screening. The non-elevated depressed mood group will be those who scored less than 3 on PHQ-2 (i.e., negative PHQ-2). Elevated depressed mood group will be those who scored 3 or more on the PHQ-2 (i.e., positive PHQ-2) and 5 or more on the follow-up PHQ-9. Those who scored 20 or more (i.e., severe depression) will be excluded from the study and offered local referral options for treatment.

Once the participants pass the breath alcohol and urine testing, and meet all the eligibility criteria, they will be scheduled for the first of two alcohol drinking sessions. Compensation for the in-person screening appointment will be \$10 for those deemed ineligible during the first hour of the appointment and \$20 for those who complete the two hour appointment, regardless of eligibility or interest in continuing with the study.

Videotaped drinking session:

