When participants arrive, they will have a short rest period during which they will be asked to consume a 150-200 calorie snack. After they consume the snack, the alcohol drinking period will begin. This part of the session will take place in a laboratory space that has been built and decorated to look like an actual bar. There will be a camcorder set up in the lab to record the whole drinking session. Beer will be the only beverage that we provide. We will provide several common brands with similar calorie (125-150) and alcohol level (approximately 4.5% ABV) for the participants to choose from (e.g., Yuengling lager, Yuengling black and tan, Smithwicks Ale). We will pour the beer of their choice into a standard glass for them to drink. The participants will be asked to drink as they usually do. They will be requested to put the glass on a food scale that we provide throughout the drinking process whenever they are not holding it.

After completing the first beer, they will take a 30 minute break before they can drink the second beer. It must be the same brand as the first beer. During the break, they may take part in recreational activities (e.g., watching television, playing games). They will be allowed to read magazines but will not be permitted to complete work during the alcohol drinking period (either academic or for a job). When they are ready after the required break time, they can start drinking the second beer. The request will be the same for them as for the first beer, and only the same type of beer as their first drink will be provided to them.

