Menstrual cycle data: Self-reports will be obtained from all women on their menstrual/gynecological status. We will include women who are cycling normally and/or on birth control pills. Three months of self-report data recording the start of their menses will be obtained prior to the laboratory sessions. This information will be obtained initially at the in-person screening and updated at the outset of each alcohol drinking session.

Symptoms: Adverse experiences are collected on standardized forms, using the *SAFTEE*³⁵ The SAFTEE includes 1) open-ended questions about any changes in physical or health problems, appearance, or activity level, and 2) yes/no responses to a specific list of symptoms for a specified time period. For each symptom reported on the SAFTEE a rater also records the severity (mild, moderate, or severe) and action taken.

Suicidality: The *Columbia Suicide Severity Rating Scale*³⁶ is a semi-structured interview that assesses past and current suicidal ideation, intent, and attempts. It will be used to monitor the safety of participants. Any participant reporting current suicidal ideation including intent to carry out a suicide attempt will be excluded from the study and the study physician, [name], will be alerted immediately.

Measures taken following the alcohol drinking period:

These measures will be administered twice per session after the conclusion of the alcohol drinking period: once immediately following the end of the alcohol drinking period and again one hour later.

Mood: The *Positive Affect and Negative Affect Scale (PANAS)*³⁷ provides a measure of current mood. Participants indicate their agreement with 20 adjectives, including 10 each to assess positive (e.g., attentive, interested) and negative affect (e.g., hostile,

Subjective effects of alcohol: The *Biphasic Alcohol Effects Scale*²⁸ is an established 14-item self-report, unipolar adjective rating scale that focuses on positively-valenced stimulant and negatively-valenced sedative effects. The *Subjective Effects of Alcohol Scale*⁴⁰ is a new measure, also made up of 14 items, which covers both positively and negatively-valenced stimulant and sedative effects of alcohol.

Craving: Craving will be assessed using two measures. The *Alcohol Urge Questionnaire (AUQ)*³⁸ an 8-item questionnaire, derived from a larger 49-item "Questionnaire of

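### Does the PANAS mood scale need a reading before the first beer?

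*Combined protocol and SAP*

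**What the plan says.** PANAS is described only in the List of instruments, under the measures taken after drinking. Those measures are to be "administered twice per session after the conclusion of the alcohol drinking period: once immediately following the end of the alcohol drinking period", with a second administration an hour later. Section 6, Survey and post-administration, agrees: the web questionnaire comes once the session is completed, and its topics are subjective response to alcohol, craving and mood, listed as three items.

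On the session day the participant rests and eats a snack. "After they consume the snack, the alcohol drinking period will begin". The items stated for session outset, or just before it, are the drinking calendar, breath alcohol, menstrual data and the pregnancy test. None is a mood scale. Mood is otherwise covered at the separate screening visit, by interview and by the PHQ, which forms the groups: "Elevated depressed mood group will be those who scored 3 or more on the PHQ-2" and 5 or more on the PHQ-9, against a PHQ-2 score below 3.

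Two limits apply to what can be read. Section 6, Overview, says "The figure below gives a timeline of the steps involved in the study", and that figure is not in the text available. The PANAS entry itself also breaks off mid-sentence. The most that can be said is that no pre-drinking mood reading is stated.

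The Specific Aims are to characterise drinking topography, compare it across the drinking and mood groups, and model it. No PANAS hypothesis, endpoint or test appears.

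**The concern.** PANAS measures state mood, and one of the two grouping factors is depressed mood. People selected for a positive PHQ may well score differently on PANAS before they touch a drink. If someone later compares PANAS after drinking between the mood groups and calls the difference a response to alcohol, the prior difference is counted as part of that response. A baseline that was never collected cannot be recovered afterwards. The protocol does plan repeated readings elsewhere: the discounting measures and the alcohol purchase task are given at screening and again after drinking. Against that pattern, the absence of an earlier PANAS reading looks like an omission. At stake is the interpretation of a set of ancillary scales. The topography aims and the sample size are not touched.

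**Working it through.** **Sample size.** The Sample size paragraph reads "we will target enrollment of up to 40 participants (~10 in each subcategory" of a 2 × 2 layout. 2 × 2 × 10 = 40, so the stated figure reproduces. Each factor therefore compares about 20 with 20. The documents give no alpha, SD, effect size or pre-post correlation. The following are assumptions: two-sided 5% level, SD 1, prior gap g of 0.25 to 1.0 SD, pre-post correlation r of 0.3 to 0.9.

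**What each contrast estimates.** Let g be the group gap in mood before drinking, assumed stable through the session. Let e1 and e2 be the group differences in response immediately after drinking and one hour later.

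- Immediate reading alone: g + e1
- One-hour reading minus immediate reading: (g + e2) − (g + e1) = e2 − e1
- Immediate reading minus a pre-beer reading (not stated in the plan): (g + e1) − g = e1

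The scheduled readings already give one contrast free of g. It describes what happens after drinking ends, not the shift from a sober level.

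**Post-drinking level read as a response.** With e1 = 0, the two-sample t test has noncentrality g × √(20/2) on 38 degrees of freedom.

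| Assumed gap g (SD) | Noncentrality | Share significant |
|---|---|---|
| 0.25 | 0.79 | 12% |
| 0.5 | 1.58 | 34% |
| 0.8 | 2.53 | 69% |
| 1.0 | 3.16 | 87% |

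As tests of a difference in level these are correct detections of a gap that was put in. They are false positives only if the result is called a response to alcohol.

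**What a pre-beer reading would gain.** Simulation (20,000 studies per setting, r 0.5 to 0.9) gives 4.8% to 5.2% for a change-score test at every gap from 0.25 to 1.0 SD. That follows directly from assuming a stable gap. Baseline-adjusted ANCOVA would not do the same between these non-randomised groups. Its residual bias is about g × (1 − r), so for g = 0.5:

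- r = 0.5: 0.5 × 0.5 = 0.25 SD, 14% significant
- r = 0.7: 0.5 × 0.3 = 0.15 SD, 10%
- r = 0.9: 0.5 × 0.1 = 0.05 SD, 6.5%

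**Precision.** The change score has SD √(2(1 − r)). The 95% half-width for the group difference is t(0.975, 38) × √(2/20) × SD = 0.640 × SD.

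- r = 0.3: SD 1.183, half-width 0.757
- r = 0.5: SD 1.000, half-width 0.640
- r = 0.7: SD 0.775, half-width 0.496
- Post-drinking level alone: half-width 0.640

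The extra reading narrows the interval only if r exceeds 0.5.

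**Unequal exposure.** Drinking is self-paced: "The participants will be asked to drink as they usually do", and "When they are ready after the required break time, they can start drinking the second beer". If exposure alone shifted mood by 0.1 SD between groups, the change-score test would reject in 6.1% to 6.8% of studies (r 0.5 to 0.7). At 0.2 SD it would reject in 9.5% to 12.5%. The shifts are assumptions. They cannot be derived from the exclusion of those who "have BMI under 18.5 or over 35": 35/18.5 = 1.89 is the ratio between two extreme individuals of equal height and says nothing about group means.

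**The case for a change.** The best case for a change is that it is cheap and cannot be made later. Twenty adjectives once per session would take a few minutes, and the pilot data are meant to support later grant applications, where someone may well want a mood response. The PHQ cannot stand in for the missing reading, because it is a different instrument given at another visit and it defines the groups. The contrast between the two post-drinking readings does not give a change from a sober level. All of that stands.

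Two parts do not carry through. First, the protocol does not call PANAS a response: the session questionnaire lists mood separately from subjective response, and the PANAS entry describes current mood. Second, the addition is not free for the stated aims. It would put a mood task between the snack and the first beer, just before the behaviour the study exists to measure. Aim 2 compares that behaviour by mood group, so any priming could differ between the groups being compared. The drinking calendar already updated at session outset is not a mood task and gives little reassurance. No figure in the documents settles how large such priming would be. A baseline would also leave time, snack, setting and expectancy mixed with alcohol, because every participant drinks beer.

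**Conclusion.** The observation is right, but no change to the plan follows. Run as written, the plan produces no wrong result on this point, because it plans no PANAS comparison and the topography aims do not use the scale. The 34%, 69% and 87% figures rest on assumed gaps of 0.5, 0.8 and 1.0 SD and on a reading of PANAS that the protocol does not state. An analyst can handle the limit at reporting: describe PANAS as a post-drinking level, or as the change from immediately to one hour after drinking, and not as change from a sober state. A pre-beer reading analysed as a change score would remove a stable prior gap. With about 20 per group it would still give only an estimate, with a half-width of 0.50 to 0.64 SD for r of 0.7 to 0.5, and it could disturb the drinking being recorded. Choosing not to add it is a defensible trade-off. The conclusion is subject to the timeline figure and the end of the PANAS entry, which could not be read. A baseline stated there would remove the question.
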